Even when DCIS patients opt to receive a less intensive treatment such as BCS without radiation therapy, they and their providers need to decide whether to undergo sentinel lymph node biopsy (SLNB). The role of SLNB for DCIS management is controversial in general and needs further scrutiny in particular if patients received BCS without radiation therapy. Significant debates continue about whether SLNB should be performed,⁶⁻⁸ with some experts advocating for its use.^{9,10} Proponents of SLNB cite concerns that occult microinvasive disease within the DCIS may not be detected histologically, with an estimated prevalence of 1.4% to 12%.¹¹ However, among DCIS patients who receive radiation therapy the likelihood of local recurrence with axillary involvement is low,¹² and routine SLNB is not recommended.¹³ Of note, radiation therapy has also been shown to control micrometastasis if present.¹⁴ On the other hand, if we plan to empower DCIS patients to choose less intensive management options, such as BCS without radiation therapy, understanding the role of SLNB will be crucial.

A systematic literature review has shown that evidence gaps exist regarding the benefits of SLNB for DCIS.¹⁵ As far as we know, no study has yet examined SLNB among DCIS patients who received BCS. Because of the current call for less intensive treatment, it is imperative to understand the benefits or harms for DCIS patients who received BCS. A large randomized controlled trial would be providing the best evidence to guide treatment recommendations, but the results would not be available for at least 10 years. Our project will use existing data to swiftly provide comprehensive information about comparative effectiveness across the DCIS care continuum in an observational study setting.

Study objectives

Using the Surveillance, Epidemiology, and End Results (SEER)-Medicare linked data, our project's overarching aims are:

Among older women with DCIS who have received BCS as their first surgery, to compare the outcomes of receiving SLNB vs. not receiving SLNB within 6 months of DCIS diagnosis:

Aim 1: We will determine associations between SLNB and acute/subacute side effects, including lymphedema, pain, and limitation of movement of upper extremity from the first BCS to 9 months post-diagnosis.

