Aim 2: We will determine associations between SLNB and long-term outcomes, including breast cancer specific mortality, ipsilateral invasive breast cancer diagnosis, subsequent mastectomy as treated recurrence, and lasting side effects, from >9 months post-diagnosis to death or the end of this study period.

Study design

We will conduct a retrospective cohort study. Using the most up-to-date SEER-Medicare database, we will examine the impact of SLNB on clinical outcomes of women with newly diagnosed DCIS among the Medicare population. The nature of SEER-Medicare linking Medicare claims records to tumor registries participating in the NCI's SEER program allows us to select study population based on precise demographic and clinical characteristics of the patients. In our study, the population is DCIS patients older than 67 years (hereafter referred to as older women) who were enrolled in a fee-for-service Medicare program and resided in the SEER areas from 1998 to 2011 (1998-2013 for Aim 2) and who were followed up to 2012 (2015 for Aim 2).

Methodology

Our study population are generated within the SEER-Medicare linked database. To identify patients with DCIS, we will use histology and behavior codes, which are converted from the ICD-O-3 codes that tumor registries are required to report to SEER for all cases.¹⁶ Specifically, we will identify breast “cancer” patients with in situ tumor behavior (behavior code = 2). DCIS patients will be further limited to those with ICD-O-3 codes consistent with epithelial origin. We select age 67 as a cut-off value because we plan to use two years of claims data to identify patient comorbidities and to control for them in our statistical models, and data is first available at age 65.

Our Aim 1 cohort will include DCIS patients who received BCS as their first surgery (i.e. excluding patients who received mastectomy first). We expect that patients who received BCS with SLNB (compared with those who received BCS without SLNB) would be more likely to end up with mastectomy, and thus would be more likely to have side effects. Findings of the associations between SLNB and mastectomy as the final treatment for DCIS would be informative. We intend to include these patients in Aim 1 so that we can provide a comprehensive picture regarding side effects of SLNB in the context of less intensive managements.

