Our Aim 2 will examine the long-term outcomes between patients who received BCS without SLNB and patients who received BCS with SLNB. Patients who received BCS in the beginning yet ended up with mastectomy for their primary DCIS will be excluded. For patients who received BCS plus RT, SLNB will not likely provide any benefits since RT is able to control small lesions. However, we plan to determine the effects of SLNB among patients who received BCS without RT, which will have important clinical implications.

The time period for defining the cohort for the Aim 1 will be between January 1998 and December 2011. Using medical claims for this cohort, we will identify any side effects within a

9-month window (from DCIS diagnosis to 9 months post-diagnosis). The time period for defining the cohort for the Aim 2 will be from January 1998 to December 2012, and patients will be followed from 9 months after DCIS diagnosis through the latest date to which data is available in SEER-Medicare. For instance, the next SEER-Medicare linked dataset will have overall mortality through December 2015, breast cancer specific mortality through December 2013, and claims data (to identify treated recurrence) through December 2014.

We identify interventions and comparators in our study using specific international classification of Diseases, Ninth Revision, (ICD-9) codes, CPT codes and HCPCS codes. We will limit our sample to DCIS patients who received BCS as their first surgery; that is, we exclude patients whose first surgery is mastectomy, because we are only interested in patients who receive less intensive treatment and their outcomes. Because SLNB is performed by a surgeon, we identify it within a window consistent with those used in prior literature to identify breast cancer surgery, that is, between the date of the first BCS and 6 months after DCIS diagnosis. We are aware that patients may receive BCS first and mastectomy later for their primary DCIS. Furthermore, we realize that SLNB may affect whether or not patients receive mastectomy.

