Based on the input of our patient and professional advisory committee members, we propose the following outcomes of interest in this project. In Aim 1 we focus on acute/sub-acute side effects. Secondary outcomes include treatment received. In Aim 2, our primary outcomes include breast cancer specific mortality, incident ipsilateral invasive breast cancer occurrence (based on ipsilateral invasive breast cancer from SEER) and treated recurrence (based on follow-up mastectomy). Secondary outcomes include overall survival and lasting side effects. Overall survival, expected to be similar, would be used as a benchmark outcome to check performance of our model.

In addition to the key exposures (interventions and comparators) and endpoints (outcomes of interest), we will further select covariates, including patient demographics, comorbidities, tumor characteristics and prior healthcare utilization, based on prior literature and our experience. We plan to include the following covariates to control for confounding. For patient demographics, we will include patient's age, sex, ethnicity, marital status and years of diagnosis. For geographical and social-economical characteristics, we will include income, education and metropolitan residence. For patient's comorbidities, we plan to include Elixhauser comorbidity index, disability index and prior hospitalization. For DCIS characters, we will include grade, size, comedonecrosis and hormone receptor status. For health care system utilization, we will consider prior influenza vaccination, physician visit, MRI use and surgeon's volume. Last, to control for other treatment patients have received, we will adjust for mastectomy and radiation therapy.

Data management and statistical analysis

We plan to create a dataset for this project. Each patient in the SEER-Medicare dataset has a unique patient identification number. Using this information, we will be able to collect patient demographics and DCIS characteristics from the SEER registry as well as claims data from Medicare on what treatment patients have received or what side effects they have experienced. We will manage the dataset in a suitable manner that fully complies with the SEER-Medicare data use rules and confidentiality.

As a secondary data analysis, we will be unable to prevent missing data from the original dataset. We do, however, set a priori exclusion and inclusion criteria for the creation of our cohort. We

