We plan to control for selection bias using propensity score matching methodology.¹⁷ Specifically, the propensity score matching will be based on the Mahalanobis distance¹⁸ calculated using age, race, residence in a metropolitan county, comorbidity, prior influenza vaccination or prior visit to a primary care physician (both as proxies for access to care), income, preoperative MRI use, and tumor characteristics. Tumor characteristics include size, grade, comedonecrosis, and estrogen receptor status. By incorporating these factors in matching, we expect to substantially decrease bias and balance the risk for outcomes of interest between the SLNB and non-SLNB groups. We will use 2: 1 matching, as prior literature indicated that this approach results in improved precision without a commensurate increase in bias.¹⁹ To ensure robust and comprehensive matching, matches will be assigned by choosing the two best non-SLNB patient matches for each SLNB patient; when two or more SLNB patients match the same control (that is, have Mahalanobis distances minimized by the same control), one will be randomly selected as a match, and this process reiterates until all SLNB patients have two matched controls. We will assess the validity of the matching by comparing risk factors between the SLNB and non-SLNB groups using χ^2 tests. The difference in outcomes between the control and intervention groups will be estimated in a Kaplan-Meier curve. We will estimate the relative risk in the propensity score matched sample using the standard method for matched-pair data.²⁰ We will use the Cox proportional hazards models to investigate the association between various factors (grade, tumor size, and estrogen receptor status) and outcomes.²¹

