For multivariable analyses, we will use conditional logistic regression models for acute/subacute side effects (primary outcomes) and treatment received (mastectomy or radiation therapy; secondary outcomes) in Aim 1, with conditioning on the matched variable. For primary outcomes, we will run 2 models, with or without controlling for treatment received. We will report adjusted odds ratios of SLNB on these outcomes. In Aim 2, we will apply time-to-event models to test whether the intervention is associated with better outcomes, including primary and secondary outcomes. We will report adjusted hazard ratios of SLNB on these outcomes. The proportional hazards assumption will be evaluated for each model using a variety of methods (evaluation of Kaplan-Meier and log(-log) survival plots, Schoenfield residuals, and covariate x time interactions). If the proportional hazards assumption is violated, we will instead use parametric survival models, using AIC and BIC to determine the best parameterization (exponential, Weibull, generalized gamma, Gompertz, lognormal, or loglog). All time-to-event models will incorporate a shared frailty term for the matching group, and will include covariates that are not balanced by matching. These models will allow us to test for association between various factors (grade, tumor size, and estrogen receptor status) and outcomes.

In order to identify suitable patient subgroups that may be able to forego SLNB, we plan to explore the following stratification schemes in Aim 2 analysis: 1. Stratify patients by receipt of radiation therapy; 2. Stratify patients by key DCIS characteristics, including grade, comedonecrosis and tumor size; 3. Stratify patients by their predicted life expectancy, given their age, sex and comorbidities.

Expected outcomes of the study

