According to our specific aims, we propose different outcomes of interest. For Aim 1, our primary outcome is the side effect occurrence within 9 months post-DCIS-diagnosis. The side effects include lymphedema, pain and limitation of movement of extremities. Our secondary outcome for Aim 1 is treatment received. We will examine the relationship between SLNB and subsequent treatment received, including mastectomy within 6 months after DCIS diagnosis and radiation therapy within 9 months after DCIS diagnosis. For Aim 2, we propose several primary outcomes. We will measure the breast cancer specific survival with the timeframe from 9 months post-diagnosis to death or end of study period. We will also assess the ipsilateral invasive breast cancer occurrence and treated recurrence, including mastectomy, within the same timeframe. For Aim 2, our secondary outcomes include overall survival (a benchmark outcome to check the performance of analytic models) and lasting side effects.

As for detailed outcome measurements, we expect to have these estimates by the end of the project: 1. the difference in baseline characteristics between the intervention and control groups and χ^2 statistics that suggests difference significance; 2. the propensity score matching results, including matched cohort and the standardized difference that indicates the balance of matching; 3. the estimate in the main analysis, for example odds ratio, rate ratio or hazard ratio, that could represent the association of intervention and outcome; 4. the estimate in the stratified analysis that could describe the association of intervention and outcome in each clinical subgroup.

Duration of the project

We are anticipating the project to be completed within 18 months of time.

Ethical concerns

As a result of the nature of our observational design, we do not anticipate any ethical concerns as we are analyzing existing data. We expect this project will be exempt from full review. However, we will make sure that no member in the project would violate the rules and confidentiality required when analyzing SEER-Medicare database.

References

2. American Cancer Society. Cancer Facts & Figure 2013. Atlanta: American Cancer Soc; 2013

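### Aim 1: SLNB exposure and the mastectomy outcome close on the same date with no rule to order them, so the SLNB–mastectomy odds ratio can be biased, up or down, when SLNB has no effect

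*Combined protocol and SAP*

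**What the plan says.** The Study objectives set the contrast for both aims: "to compare the outcomes of receiving SLNB vs. not receiving SLNB within 6 months of DCIS diagnosis". The Methodology section places SLNB in a window, "that is, between the date of the first BCS and 6 months after DCIS diagnosis". Under Expected outcomes of the study, the Aim 1 secondary outcome is described thus: "We will examine the relationship between SLNB and subsequent treatment received, including mastectomy within 6 months after DCIS diagnosis". Exposure and outcome windows therefore close on the same date.

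Women who start with BCS and convert to mastectomy are kept in Aim 1 on purpose. The Methodology section expects that women with SLNB "would be more likely to end up with mastectomy, and thus would be more likely to have side effects". It also notes that "we realize that SLNB may affect whether or not patients receive mastectomy", but it does not consider the reverse, that conversion may bring an SLNB with it.

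Under Data management and statistical analysis, "matches will be assigned by choosing the two best non-SLNB patient matches for each SLNB patient", using patient, tumor and access-to-care variables. Mastectomy is then analyzed by conditional logistic regression with SLNB as a fixed yes/no exposure. The side-effect outcomes are handled separately: "For primary outcomes, we will run 2 models, with or without controlling for treatment received".

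On a smaller point, the Aim 1 side-effect window opens at first BCS in the Study objectives and at DCIS diagnosis in the Methodology section.

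**The concern.** The word subsequent shows that SLNB is meant to come first, but nothing in the matching or the model makes it so. Two errors follow.

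- **Upward.** A woman without SLNB at first BCS who has it at or after the decision to convert is classed as exposed. Her mastectomy is then credited to an SLNB that followed from it.
- **Downward.** A woman who keeps her breast has the whole window in which to receive a later SLNB. An early converter has less time to receive one before converting. Exposure therefore accumulates preferentially among women without the event.

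Both come from when exposure is counted, so balance on baseline covariates neither reveals nor removes them. The plan predicts more mastectomy with SLNB and uses that to explain side effects. An upward artefact would look like confirmation, and a downward one could hide a real association.

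**Working it through.** The plan states no odds ratio, event rate or sample size for this analysis, so there is no figure to reproduce. The check asks what odds ratio the planned definition returns when SLNB has no effect on mastectomy.

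**Inputs (all assumed; the documents give none)**
- s: share with SLNB at first BCS, the same in converters and breast-keeping women
- q: share of converters without earlier SLNB who get it at or after the decision to convert
- g: share of breast-keeping women without SLNB at first BCS who get it later in the window
- f: share of g that is reached before conversion
- Q = fg + (1−fg)q: share of converters without SLNB at first BCS who end up classed as exposed

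**Formula.** The odds of being classed as exposed are [s+(1−s)Q]/[(1−s)(1−Q)] in converters and [s+(1−s)g]/[(1−s)(1−g)] in breast-keeping women. Their ratio is

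null OR = [s+(1−s)Q](1−g) / {[s+(1−s)g](1−Q)}.

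The conversion share cancels.

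**Upward part alone (g = 0).** At s = 0.2 and q = 25%: (0.2 + 0.8×0.25)/(0.2×0.75) = 0.40/0.15 = 2.67.

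| s | q=10% | q=25% | q=50% |
|---|---|---|---|
| 0.1 | 2.11 | 4.33 | 11.0 |
| 0.2 | 1.56 | 2.67 | 6.00 |
| 0.3 | 1.37 | 2.11 | 4.33 |

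**Both parts (s = 0.2, g = 10%).** At q = 5% and f = 0.4: Q = 0.04 + 0.96×0.05 = 0.088, and the OR is (0.2704×0.9)/(0.28×0.912) = 0.95.

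| q | f=0 | f=0.4 | f=0.8 |
|---|---|---|---|
| 0 | 0.64 | 0.78 | 0.92 |
| 5% | 0.81 | 0.95 | 1.11 |
| 10% | 1.00 | 1.15 | 1.31 |

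The sign depends on q, g and f together.

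**Matched analysis.** A simulation used 15,000 women and 60 replicates per setting, with 2:1 matching on a measured risk score and a conditional logistic model. SLNB at first BCS was set at about 15%, mastectomy at about 10%, and SLNB had no effect. As the plan is written, the OR was 1.60, 2.79 and 6.43 for q = 10%, 25% and 50% with no other later SLNB. It was 0.75 with q = 0 and a 10% chance of later stand-alone SLNB. The true null was rejected in 98% to 100% of these runs. With no late SLNB the OR was 1.01. With exposure fixed at first BCS it was 1.01 in every setting, with 5% to 7% rejection.

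**The case against.** The best defence is that the plan says subsequent and speaks of associations. That establishes intent. It does not classify an SLNB done on or after the mastectomy date, and it gives women without SLNB no date from which to count.

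Enforcing the word does not settle the matter either. Suppose order is applied only to the outcome, so that an SLNB at mastectomy counts as exposed without the event. The null OR is still 1.05 to 1.52 for q = 10% to 50% (s = 0.15, 10% conversion, g = 0). If instead SLNB must precede mastectomy, the upward part goes. What remains is the q = 0 row above: 0.64 to 0.92, reaching 1 only at f = 1.

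It is also fair to say that the size is unknown. The large values come from a chosen grid, and bias is nil if all SLNBs are done at first BCS. That stands, and it is why the dates should be tabulated.

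A reader might infer that the primary side-effect results are compromised too, and that exposure should be redefined throughout Aim 1. The material does not support that. Take s = 0.2, 15% conversion, and assumed side-effect risks of 10% without and 20% with mastectomy. The null side-effect OR in the model without treatment received is then 1.03 to 1.28 for q = 5% to 50% (g = 0). The plan also has a model that includes treatment received. In that model the bias is about nil, but only because the example lets later SLNB act on side effects solely through mastectomy. Against this, moving women with later SLNB into the control group would dilute a real harm. If all of them carry the doubled risk, a true risk ratio of 2 becomes 2/[1+mq+(1−m)g], where m is the conversion share. With m = 15% and f = 0 this is 1.97 (q = 10%, g = 0) to 1.72 (q = 50%, g = 10%).

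**Conclusion.** The concern holds for the Aim 1 mastectomy outcome. The windows close together, no rule orders them, and a fixed-exposure conditional logistic model can then return an odds ratio away from 1 when SLNB does nothing. At s = 0.2 the illustrations run from 0.64 to 6.00, all on assumed frequencies.

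Two stronger readings are not supported. One is that the plan will overstate the link with mastectomy: the documents give no timing frequencies, so no direction can be stated. The other is that the OR must fall below 1 whenever q is less than g: that holds only at f = 0, and q = 5% with g = 10% gives 1.11 at f = 0.8. Aim 2 is outside the point, since its follow-up starts at 9 months and it excludes women who convert for the primary DCIS. The outcome is secondary, but the plan leans on it to explain side effects, so it should be fixed before analysis.

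**What to change.** For the Aim 1 mastectomy analysis only:

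- Set the index date at first BCS in both groups and define exposure as SLNB at that first BCS.
- Count mastectomy only after that date, to 6 months after diagnosis, and keep women with later SLNB in the no-SLNB group.
- Keep the 6-month exposure definition as a sensitivity analysis.
- Tabulate how many SLNBs fall after first BCS, and how many fall on or after the mastectomy date. This shows whether the problem is material.
- Do not rely solely on a rule that SLNB must precede mastectomy; it leaves some downward bias when g > 0 and f < 1.

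For the primary side-effect outcomes, keep the planned 6-month exposure and add the first-BCS definition as a sensitivity analysis. Reconcile the two stated starts of the side-effect window.

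**Cost.** Protocol wording and date logic on claims; the 2:1 matching method and the conditional logistic model stay. The mastectomy contrast becomes SLNB at first BCS, which differs from the contrast in the Study objectives, and it needs its own matched set. The exposed group shrinks by L/(s+L), with L = (1−s)[mq+(1−m)g]. At s = 0.2, m = 15% and f = 0 the loss is 0.006/0.206 = 2.9% (q = 5%, g = 0) to 0.128/0.328 = 39.0% (q = 50%, g = 10%).

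### SLNB counts at any operation up to month 6, but repeat BCS is neither matched nor adjusted, so the Aim 1 odds ratios may be biased upward by an unknown amount

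*Combined protocol and SAP*

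**What the plan says.** **Exposure.** The Methodology section identifies SLNB from claims in the window "between the date of the first BCS and 6 months after DCIS diagnosis". The window is not tied to the first operation.

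**Matching.** Data management and statistical analysis lists the matching variables as "age, race, residence in a metropolitan county, comorbidity, prior influenza vaccination or prior visit to a primary care physician", then "income, preoperative MRI use, and tumor characteristics". On the last item it adds: "Tumor characteristics include size, grade, comedonecrosis, and estrogen receptor status". No surgical variable appears, and margin status is absent.

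**Treatment covariates.** The covariate paragraph of Methodology ends: "Last, to control for other treatment patients have received, we will adjust for mastectomy and radiation therapy". The modelling paragraph likewise defines treatment received in Aim 1 as mastectomy or radiation. It plans two models for each primary outcome, one with and one without that adjustment.

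**Further surgery.** Methodology expects SLNB patients to go on to mastectomy more often, and for that reason to have more side effects. It keeps these women in Aim 1 and excludes from Aim 2 those whose primary DCIS ended in mastectomy. Mastectomy is the only second breast operation that the plan discusses. Re-excision, the number of operations, and whether SLNB was done at the first or a later operation are not mentioned.

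**The concern.** A woman who has one BCS has one breast-conserving operation at which SLNB can be done. A woman who returns for a second BCS within the window has two. If some SLNBs are done at the second operation, the exposure definition itself tends to concentrate repeat surgery in the SLNB group.

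This matters for Aim 1 if a second breast operation generates claims for the primary outcomes (lymphedema, pain, limited arm movement). Study objectives counts side effects over a period ending "limitation of movement of upper extremity from the first BCS to 9 months post-diagnosis"; Methodology uses a "9-month window (from DCIS diagnosis to 9 months post-diagnosis"). On either start date, claims that arise between the first operation and a later SLNB are counted against SLNB.

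The plan accepts this reasoning for mastectomy and fits paired models because of it, but does not extend it to repeat BCS. At stake is an odds ratio moderately above 1 being read as harm from SLNB when part of it reflects more breast surgery. In Aim 2, a repeat BCS may signal an incomplete first excision, which could bear on later ipsilateral invasive cancer and treated recurrence.

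**Working it through.** The plan states no re-excision rate, no SLNB rate by operation and no side-effect risk, so there is no figure to reproduce. **Every input below is an assumption.** The calculation is crude (no matching) and sets the true SLNB effect to none.

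**Notation.** q = share of women with repeat BCS; s1, s2 = probability of SLNB with one operation and with repeat BCS; r1, r2 = side-effect risk in those two strata.

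**Formulas.**
- P(SLNB) = (1 − q)·s1 + q·s2
- Repeat BCS among SLNB women: a = q·s2 / P(SLNB)
- Repeat BCS among controls: b = q·(1 − s2) / (1 − P(SLNB))
- Risk in a group = r1 + (r2 − r1) × its repeat-BCS share
- Spurious odds ratio = odds(SLNB) / odds(control)

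**Central case** (q = 25%, s1 = 15%, s2 = 30%, r1 = 5%, r2 = 10%).
- P(SLNB) = 0.75 × 0.15 + 0.25 × 0.30 = 0.1875
- a = 0.075 / 0.1875 = 40.0%; b = 0.175 / 0.8125 = 21.5%
- Risks: 0.05 + 0.05 × 0.400 = 7.00%; 0.05 + 0.05 × 0.2154 = 6.08%
- Odds ratio = (0.0700 / 0.9300) / (0.0608 / 0.9392) = **1.16**

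**Range** over q 20–30%, s1 10–15%, s2 25–30%, r1 4–10%, r2 10–15%:
- Lowest: **1.00**, when r1 = r2 = 10%, so repeat BCS carries no extra risk.
- Highest: **1.57**, at q = 25%, s1 = 10%, s2 = 30%, r1 = 4%, r2 = 15%. Here a = 50.0%, b = 20.6%, and the risks are 9.50% and 6.26%.

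**Dependence on the SLNB gap** (other central inputs unchanged):

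| s1 vs s2 | Spurious odds ratio |
|---|---|
| 15% vs 30% | 1.16 |
| 15% vs 20% | 1.06 |
| 15% vs 15% | 1.00 |
| 15% vs 10% | 0.93 |

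**The window mechanism alone.** Suppose SLNB at the first operation is 20% whether or not a repeat BCS follows, and women without it have a further 20% chance at the repeat operation. Then s2 = 0.20 + 0.80 × 0.20 = 36%. With q = 25%, repeat BCS is 37.5% of SLNB women and 21.1% of controls. At a base risk of 10%, the odds ratio is 1.08 if repeat BCS multiplies the risk by 1.5, and 1.16 if it doubles it. With no extra SLNB at the repeat operation, it is 1.00.

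**The case against.** The strongest reply is that a gap in a covariate list is not a bias. Controls can also have repeat BCS, and their side effects are counted too, so only an imbalance that survives matching distorts the odds ratio. Size, grade, comedonecrosis and preoperative MRI are matched, and surgeon's volume is a listed covariate; these may absorb part of any imbalance. The direction also rests on an assumption: if SLNB were less common among re-excised women, the bias would reverse. A second operation that is a mastectomy is controlled in one of the two Aim 1 models. If a woman returned only to have SLNB, the effects of that operation belong to SLNB.

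Most of this stands, and it limits the claim. It does not remove it. Matching on tumor features does not take away the extra occasion for exposure. The planned balance check does not name repeat BCS, so nothing in the plan ensures that an imbalance would be seen.

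A reader might infer that side effects of second operations are in fact being attributed to SLNB, that the odds ratios will exceed 1, or that Aim 2 is confounded. The documents support none of these as fact, since they give no rate from which to derive the imbalance or the effect of repeat BCS. For Aim 2, excluding women who ended with mastectomy for the primary DCIS already removes one route by which an incomplete first excision could enter.

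**Conclusion.** The concern holds as a possible bias of unknown size. The gap is plain in the text: the exposure window admits SLNB at a later operation, and repeat BCS is in neither the matching nor the adjustment set. Upward bias in the Aim 1 odds ratios follows if two conditions hold together: repeat BCS remains more frequent in the SLNB group after matching, and it raises claims for at least one primary outcome. The illustrative 1.16, with its span of 1.00 to 1.57, shows that the effect could be anything from nil to material. It is not an estimate for this study, because it rests wholly on assumed inputs and ignores matching. For Aim 2, no size or direction can be given. The change is worth making because it is cheap and because the plan already accepts the same argument for mastectomy.

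**What to change.** 1. **Record and report.** From the claims, identify each repeat BCS and its date relative to SLNB. Report its frequency by group, before and after matching.
2. **Extend the planned paired models.** Add repeat BCS to the treatment-received set, so that the Aim 1 models with and without treatment received also cover it. Separate repeat BCS before or on the day of SLNB (a potential confounder) from repeat BCS after SLNB (a possible mediator). Add a with/without comparison in Aim 2.
3. **Sensitivity analysis.** Define exposure as SLNB on the day of the first BCS, exclude women whose first SLNB came later, and repeat the analysis in women with a single BCS. The repeat is needed because the exclusion alone removes some re-excised women from the comparison. In the window example above, repeat BCS would be 25% of the exposed and 0.20 / (0.20 + 0.75) = 21.1% of controls, leaving an odds ratio of 1.04 at a doubled risk.

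Matching controls at the same operation number looks attractive but is not a simple addition. The operation count would be constant within a matched set and would drop out of the conditional logistic model, and controls could still have SLNB later in the window.

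**Cost.** A little more analysis on claims the project already plans to use, and fewer exposed women in the sensitivity analysis. Adjusting for a repeat BCS that follows SLNB could over-adjust, which is why both models should be reported.
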